## **13 STUDY CONDUCT RESPONSIBILITIES**

### **13.1 PROTOCOL AMENDMENTS**

Any changes in research activity, except those necessary to remove an apparent, immediate hazard to the participant in the case of an urgent safety measure, must be reviewed and approved by the Chief Investigator.

Amendments to the protocol must be submitted in writing to the appropriate REC and local R&D for approval prior to participants being enrolled into an amended protocol.

### **13.2 PROTOCOL VIOLATIONS AND DEVIATIONS**

Prospective protocol deviations, i.e. protocol waivers, will not be approved by the sponsor and therefore will not be implemented, except where necessary to eliminate an immediate hazard to study participants. If this necessitates a subsequent protocol amendment, this should be submitted to the REC and local R&D for review and approval if appropriate.

Protocol deviations will be recorded in a protocol deviation log and logs will be submitted to the sponsors every 3 months. Each protocol violation will be reported to the sponsor within 24 hours of becoming aware of the violation.

### **13.3 SERIOUS BREACH REQUIREMENTS**

A serious breach is a breach, which is likely to affect to a significant degree:

- (a) the safety or physical or mental integrity of the participants of the study; or
- (b) the scientific value of the study.

If a potential serious breach is identified by the Chief investigator, Principal Investigator or delegates, the sponsors ([[contact]](mailto:[contact])) must be notified within 24 hours. It is the responsibility of the sponsors to assess the impact of the breach on the scientific value of the study, to determine whether the incident constitutes a serious breach and report to regulatory authorities and research ethics committees as necessary.

### **13.4 STUDY RECORD RETENTION**

All study documentation will be kept for a minimum of 5 years from the protocol defined end of study point. When the minimum retention period has elapsed, study documentation will not be destroyed without permission from the sponsor.

### **13.5 END OF STUDY**

Clinical interventions expected to finish 31/12/2017. End of the study will be once final analysis has been completed.

The Investigators and sponsor have the right at any time to terminate the study for clinical or administrative reasons.

The end of the study will be reported to the REC within 90 days, or 15 days if the study is terminated prematurely. The Investigators will inform participants of the premature study closure and ensure that the appropriate follow up is arranged for all participants involved.

A summary report of the study will be provided to the REC within 1 year of the end of the study.

### **13.6 INSURANCE AND INDEMNITY**

The sponsor is responsible for ensuring proper provision has been made for insurance or indemnity to cover their liability and the liability of the CI and staff. The sponsor, as part of the United Kingdom's Nation Health Service, and will have the benefit of NHS Indemnity.

## **14 REPORTING, PUBLICATIONS AND NOTIFICATION OF RESULTS**

### **14.1 AUTHORSHIP POLICY**

Ownership of the data arising from this study resides with the study team. On completion of the study, the study data will be analysed and tabulated, and a clinical study report will be prepared in accordance with ICH guidelines.

### **14.2 PUBLICATION**

The results of our research will be disseminated in the following ways:

1. Summary disseminated to NHS Lothian communication systems including EMERGE intra- and internet sites and all participating sites
2. A media summary
3. Presentation at local and national educational, clinical and research meetings and international research meetings
4. Publication in peer reviewed journals
5. Research report disseminated to NHS Lothian R&D, NHS Research Scotland, and CHSS.

The clinical study report will be used for publication and presentation at scientific meetings. Investigators have the right to publish orally or in writing the results of the study.

### **14.3 PEER REVIEW**

The IPED study received grant funding from CHSS where it underwent peer review and was successfully awarded funding. The patient information sheet, consent form and patient symptom diary and patient satisfaction and compliance questionnaire were reviewed by the EMERGE patient and public involvement group.

### *List of abbreviations*

AE	Adverse Event
AMU	Acute Medical Unit (or equivalent)
BP	Blood Pressure
CHB	Complete Heart Block
CI	Chief investigator
CRF	Case Report Form
ECG	Electrocardiogram
ED	Emergency Department
EPS	Electrophysiology study
GP	General Practitioner
ICD	Implantable Cardioverter Defibrillator
IPED	Investigation of Palpitations in the ED
IQ	Interquartile
MACE	Major Adverse Cardiac Event
NHS	National Health Service
SAE	Serious Adverse Event

## ***1. Introduction***

The following document contains a description of the planned analysis for the IPED study. The full description of the study is available from the study protocol. However, in brief, this study aims to determine if using a smart phone event recorder will allow Emergency Department (ED) patients who have presented with palpitations or pre-syncope to record their Electrocardiogram (ECG) tracing if they have a further episode increasing the rate of underlying rhythm diagnosis.

## ***2. Study design***

This is a multi-centre hospital ED/Acute Medical Unit (AMU) open label, randomised controlled trial of participants aged 16 years or over presenting with an episode of palpitations or pre-syncope and whose underlying ECG rhythm during these episodes remains undiagnosed after ED assessment. Participants will be followed-up at 90 days using hospital records, contacting participant General Practitioner (GP) and also by contacting the participants themselves. This study is expected to take around 18 months to complete from first participant recruited to last participants' 90-day follow-up.

### **2.1. Number of participants**

242 consecutive participants aged 16 years or over presenting with an episode of palpitations or pre-syncope and whose underlying ECG rhythm during these episodes remains undiagnosed after ED assessment shall be recruited into the study. Recruitment will last around 15 months.

### **2.2. Study endpoints**

The primary endpoint is the symptomatic rhythm detection rate of a smart phone based event recorder (AliveCor Monitor) for symptomatic rhythm detection at 90 days versus standard care for participants presenting to the ED with palpitations and pre-syncope with no obvious cause in the ED.

The secondary endpoints are:

1. Symptomatic rhythm detection rate of a smart phone based event recorder for cardiac arrhythmia detection at 90 days versus standard care.
2. Time to detection of symptomatic rhythm using a smart phone based event recorder versus standard care.
3. Time to detection of cardiac arrhythmia rhythm using a smart phone based event recorder versus standard care.
4. Number of participants treated or (planned for treatment) for cardiac arrhythmia in participants using a smart phone based event recorder versus standard care.

5. Participant satisfaction and monitor compliance.
6. Cost effectiveness analysis.
7. Serious outcomes at 90 days: all cause death and major adverse cardiac events (myocardial infarction, life-threatening arrhythmia, insertion of a pacemaker or internal cardiac defibrillator, insertion of pacing wire).

### **2.3. Adverse events**

A secondary endpoint for the study is serious outcomes at 90 days: all cause death and major adverse cardiac events [MACE] (myocardial infarction, life-threatening arrhythmia, insertion of a pacemaker or internal cardiac defibrillator, insertion of pacing wire). This data will therefore be routinely collected as part of the study and not recorded as an Adverse Event (AE). Hospital admission will also not be recorded as an AE. The only AEs recorded will be those directly related to the use of the smart phone based event recorder and application.

## ***3. Statistical methods from protocol***

Descriptive analysis of participant characteristics shall be presented split by study arm. Baseline to 90 day change in diagnostic yield between the two study arms will be analysed using two sample t-tests or non-parametric equivalent as appropriate. Log-rank tests and Kaplan-Meier curves shall be used to examine if the smartphone recorder has an effect on detecting symptomatic rhythm and cardiac arrhythmia separately up to 90 days versus standard care. Categorical variables will be compared using a  $\chi^2$  test (and  $\chi^2$  test for trend if appropriate). All participants will be analysed on an intention to treat basis.

## ***4. Study methods***

### **4.1. Randomisation and treatment allocation**

Participants will be equally distributed between the two study arms. Randomisation will be by block randomisation by site. An equal number of sealed opaque envelopes containing either 'Standard Care plus Device' or 'Standard Care' cards will be prepared by a central administrator not involved in the study. These will then be randomly labelled with site-specific study participation numbers and sent to each local study team. Participants eligible for inclusion will be randomised by the local study team by taking the next lowest consecutively numbered sealed opaque envelope. There will be no stratification or minimization factors.

Participants will be allocated either to (a) STUDY arm; standard care plus the use of a smart phone based event recorder or (b) CONTROL arm; standard care, depending on the group allocated in the study envelope.

## **4.2. Study assessments**

### **4.2.1. Screening and baseline assessments**

Potentially eligible participants will be identified and assessed for study inclusion by the attending clinician. Written consent will be taken and participants will have a Case Report Form (CRF) completed and a 12-lead ECG taken if not already performed by the clinical team.

Participants in both groups will be admitted, referred or discharged by the treating clinician according to current local hospital protocols.

### **4.2.2. Follow up assessments**

Participants in both groups will be followed up at 90 days through hospital record systems (paper or electronic depending on local policy), GP records and by telephone by the local study team. Participants will also be asked to complete a standardised written questionnaire and will receive a follow-up telephone call from the local study team enquiring about symptoms and contact with medical services. Study arm participants will also be asked about satisfaction and compliance with the heart monitor.

Participants allocated to the Study arm may be contacted by telephone by the local research team shortly after randomisation in the event of them requiring further training or setting up of the device.

If a participant allocated to the Study arm gets an episode of palpitations or pre-syncope and is able to record an AliveCor Heart Monitor ECG during the episode, the participant will email the ECG recorded by the AliveCor app directly to the co-ordinating Edinburgh research team at a convenient time to the participant and to a secure nhs.net email address.

The co-ordinating Edinburgh research team will review the ECG and will contact the local study team to arrange follow-up if required. If specialist follow-up of the ECG tracing is not required then the local study team will write to the participant informing them of this and ask them to arrange follow up with their general practitioner who will be contacted with the report. The participant and GP will not be contacted further should participants record other similar ECGs that similarly do not require specialist follow-up.

If the participant records a serious significant arrhythmia during the study period, the local study team will alert the participant immediately by telephone, and refer them urgently to their local Emergency Department or cardiac electrophysiology service (as per local protocol).

### **4.2.3. Participant symptom diary, satisfaction and compliance**

Participants will be asked to log any symptoms along with the time and date, type of symptom and whether they were able to record an ECG during the symptoms, in a participant symptom diary. They will return this diary to the local research team along with the participant satisfaction and compliance questionnaire, and smart phone based event recorder at the end of the 90 days. Participants will be phoned at 90 days by the local study team to remind them to complete the participant satisfaction and compliance questionnaire and to return this to the local study team with the symptom diary and smart phone based event recorder. The compliance questionnaire is designed to capture whether participants had the device with them and were able to record a heart tracing during symptoms. Detail the specific study assessments to be performed and the time points during the study - split by visit number if appropriate for clarity. It may be appropriate to prepare a table of assessments by visit.

## ***5. General Considerations***

### **5.1. Overall**

For all analyses, unless otherwise specified, participants shall be analysed according to treatment received, irrespective of the treatment group they were allocated to, with the exception of AE/SAEs. An additional table will be provided on whether the participant took part in the study and if they did not then their AE/SAEs will be included as part of the control group.

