### **6.2 STUDY ASSESSMENTS**

Potentially eligible ED and AMU participants will be identified and assessed for study inclusion by the attending clinician. Written consent will be taken and participants will have a Case Report Form (CRF) completed and a 12-lead ECG taken if not already performed by the clinical team.

All STUDY arm participants will be given an AliveCor Heart Monitor and trained in the use of the device and app in the ED or AMU by the research team.

CONTROL arm participants will receive no other intervention.

Participants in both groups will be admitted, referred or discharged by the treating clinician according to current local hospital protocols.

Participants in both groups will be followed up at 90 days through hospital record systems (paper or electronic depending on local policy), GP records and by telephone by the local study team. Participants will also be asked to complete a standardised written questionnaire and will receive a follow-up telephone call from the local study team enquiring about symptoms and contact with medical services. Participants will also be asked about satisfaction and compliance with the heart monitor.

Participants allocated to the Study arm may be contacted by telephone by the local research team shortly after randomisation in the event of them requiring further training or setting up of the device. For example, this may be necessary if a participant does not have their app store password with them in the ED or AMU. If a local electronic patient record system is available, then a research alert will be placed on this stating that the participant has consented to be part of the IPED study.

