### **8.2 PROPOSED ANALYSES**

Descriptive analysis of participant characteristics shall be presented split by study arm. Baseline to 90 day change in diagnostic yield between the two study arms will be analysed using two sample t-tests or non-parametric equivalent as appropriate. Log-rank tests and Kaplan-Meier curves shall be used to examine if the smartphone recorder has an effect on detecting symptomatic rhythm and cardiac arrhythmia separately up to 90 days versus standard care. Categorical variables will be compared using a  $\chi^2$  test (and  $\chi^2$  test for trend if appropriate). All participants will be analysed on an intention to treat basis.

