### **6.2. Baseline demographic statistics**

The following participant details shall be presented split by allocated study arm. Where data are continuous the mean, standard deviation, median, interquartile (IQ) range and range shall be presented and where data are binary or categorical the frequency and percentage shall be presented:

- Participant demographics
- History of presenting episode
- Past medical history
- Examination
- Admission ECG
- Management

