### **6.3. Primary outcome**

The baseline to 90 day change in diagnostic yield (i.e. presence/absence symptomatic rhythm detection) of a smart phone based event recorder compared with standard care only shall be analysed using a comparison of proportions test.

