### **6.4. Secondary outcomes**

1. The baseline to 90 day change in cardiac arrhythmia detection (i.e. presence/absence) of a smart phone based event recorder compared with standard care only shall be analysed using comparison of proportions test.
2. A log-rank test and Kaplan-Meier curves shall be used to examine if the smartphone recorder has an effect on time to first detection of symptomatic rhythm up to 90 days versus standard care only.
3. A log-rank test and Kaplan-Meier curves shall be used to examine if the smartphone recorder has an effect on time to first detection of cardiac arrhythmia rhythm up to 90 days versus standard care only.

4. The number of participants treated (or planned for treatment) for cardiac arrhythmia in those using a smart phone based event recorder versus standard care only shall be analysed using a comparison of proportions test.
5. Participant satisfaction questionnaire responses shall be compared between study arms using  $\chi^2$  test(s) (and  $\chi^2$  test(s) for trend if appropriate). A similar analysis shall be performed for participant compliance questionnaire responses.
6. The number of participants recorded for each of the following shall be collated. If appropriate and numbers allow, a two-sample t-test (or non-parametric equivalent as appropriate) shall be used to compare study arms where the outcome of interest is continuous. However if the numbers are to be treated as categorical then a  $\chi^2$  test (and if appropriate,  $\chi^2$  test for trend) shall be used to compare study arms:
  - Number of ED presentations (except index visit) due to palpitations/pre-syncope.
  - Number of inpatient hospital days (over all admissions) due to palpitations/pre-syncope.
  - Number of outpatient presentations due to palpitations/pre-syncope.
  - Number of GP presentations due to palpitations/pre-syncope (via phone follow-up).
  - Number of TRAK ECGs due to palpitations/pre-syncope.

A comparison of the overall cost-effectiveness of the smart phone based event recorder and standard care shall be provided using a two-sample t-test (or non-parametric equivalent as appropriate) between study arms. The costing scope will include primary care, secondary care and community NHS costs which shall be provided separately by the CI for analysis.

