7. The number of participants recording at least one serious outcome at 90 days in those using a smart phone based event recorder compared to standard care only shall be examined by a comparison of proportions test. Following on from this the number of serious outcomes at 90 days between the two study arms shall be examined using a  $\chi^2$  test (and  $\chi^2$  test for trend if appropriate).

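### SAP 5.1 makes an undefined treatment-received grouping the default for the primary and secondary comparisons, against the intention-to-treat rule in protocol 8.2 and SAP 3

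*SAP*

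**What the plan says.** Protocol 8.2 states: "All participants will be analysed on an intention to treat basis". SAP 3, which restates the protocol's methods, repeats that sentence.

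SAP 5.1 then gives its own default for every analysis not otherwise specified: "participants shall be analysed according to treatment received, irrespective of the treatment group they were allocated to". The only stated exception is AE/SAEs. A further sentence places the AE/SAEs of people who did not take part in the study in the control group.

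SAP 6.3 says only that the recorder "compared with standard care only shall be analysed using a comparison of proportions test"; it names no rule for assigning participants to arms. SAP 6.4 names none either. Its items 4 and 7 describe the groups as "in those using a smart phone based event recorder versus standard care only" and "in those using a smart phone based event recorder compared to standard care only". By contrast, SAP 6.2 does specify a grouping for the baseline tables: "The following participant details shall be presented split by allocated study arm".

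Neither document defines treatment received. Protocol 6.2 says "All STUDY arm participants will be given an AliveCor Heart Monitor and trained in the use of the device and app", and also allows for set-up to be completed by telephone after randomisation. SAP 4.2.3 says: "The compliance questionnaire is designed to capture whether participants had the device with them and were able to record a heart tracing during symptoms".

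**The concern.** A statistician who follows the SAP as written would run the primary test on groups formed by what happened after randomisation, while the baseline tables would describe the randomised groups. The protocol calls for the opposite, and no reason is given for the change.

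The undefined term adds to the problem. If received means handed over, few people would change group. If it means used, a study-arm participant with no further episode has nothing to record and could be counted as a control. Membership of the device group would then depend partly on the outcome, and the comparison would plausibly be biased towards the device. The direction could also reverse: a rhythm captured during an admission, before the app was set up, might count as a control detection. Because the trial is open label, a definition settled late could be chosen with results in view.

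The AE/SAE exception does not protect secondary endpoint 7, because SAP 2.3 says serious outcomes are not recorded as AEs. The sentence on non-participants is unclear in its own right. Taking part is undefined, and SAP 2.3 records only device-related AEs, so a device-related event could be tabulated under standard care.

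**Working it through.** **Step 1: which rule governs the primary analysis.** SAP 5.1 yields only where another section specifies a grouping. SAP 6.2 does so; SAP 6.3 and 6.4 do not. One could treat SAP 3 as the overriding text, but it covers all participants, so the SAP 5.1 default would then apply to nothing. On either view two opposite rules stand in the same SAP with no order of precedence.

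**Step 2: the plan's own figure.** Protocol 8.1 gives 25% v 10% detection, 80% power and 110 per group. Alpha is not stated; I assume two-sided 5%. Exact power of Fisher's test is 79.9% at 109 and 80.4% at 110 per group, so 110 is reproduced. Adding 10% gives 110 × 1.10 = 121. The choice of analysis rule does not change this number.

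**Step 3: what reclassification could do.** From the documents: 121 per arm, control detection pc = 10%, planned study-arm detection P = 25%. Assumed, because the documents are silent: a fraction f of the study arm is moved to control, and those moved have detection rate q. No control moves the other way.

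Expected as-treated difference = (P − f·q)/(1 − f) − (pc + f·q)/(1 + f).

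*No true effect* (P = pc = 10%), for example f = 10% and q = 0%:
- Device group: 0.10/0.90 = 11.1%. Control group: 0.10/1.10 = 9.1%. Difference: +2.0 points.
- Average group sizes: 121 × 0.9 = 108.9 and 121 × 1.1 = 133.1. The pooled rate is 10%.
- Standard error under the null: √(0.09 × (1/108.9 + 1/133.1)) = 0.0388. Actual standard error: 0.0391.
- Rejection probability: Φ((0.0202 − 1.96 × 0.0388)/0.0391) + Φ((−0.0202 − 1.96 × 0.0388)/0.0391) = about 7.7% + 0.7% = 8.4%.

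Exact enumeration, with the number moved ~ Binomial(121, f) and a pooled z-test at |z| > 1.96, gives:

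| Detection in those moved (q) | Expected difference, f = 5 / 10 / 20% | Type I error, f = 5 / 10 / 20% |
|---|---|---|
| 0% | +1.0 / +2.0 / +4.2 points | 5.8 / 8.4 / 19.0% |
| 5% | +0.5 / +1.0 / +2.1 points | 5.2 / 5.9 / 8.6% |
| 10% | 0 / 0 / 0 | 5.0 / 5.0 / 5.0% |
| 20% | −1.0 / −2.0 / −4.2 points | 5.7 / 7.8 / 17.2% |

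Analysis by allocation gives 5.0% in every row. In the last row most rejections favour control: 4.3, 7.1 and 17.1 percentage points of the totals. Simulation of 200,000 trials per scenario for q = 0, 5 and 10% agreed within 0.2 points.

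*Planned effect* (P = 25%, pc = 10%, f = 10%). By allocation the difference is 15 points. As treated:
- q = 0%: 0.25/0.9 − 0.10/1.1 = 27.8% − 9.1% = 18.7 points.
- q = 10%: 0.24/0.9 − 0.11/1.1 = 26.7% − 10.0% = 16.7 points.
- q = 25%: 0.225/0.9 − 0.125/1.1 = 25.0% − 11.4% = 13.6 points.

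**The case against.** The textual conflict is hard to dispute, so the best defence concerns its consequences.

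- **Using may simply be an arm label.** The same phrasing appears in the protocol's objective 7 and secondary endpoint 4 and in SAP 2.2. Protocol 5.5.2 and SAP 4.1 define the study arm in terms of use of the recorder. This stands: the wording of items 4 and 7 makes a used reading possible but does not establish it.
- **Few people may move.** Monitors are given to all study-arm participants at enrolment, and exclusion 9 removes those unable or unwilling to use them. If received means handed over, f is near zero and the bias is probably small. This stands too. Under the used reading f could exceed 20%. The 5–20% range therefore comes from neither document and should not be read as a forecast.
- **The reversal is speculative.** Set-up is to be completed shortly after randomisation, daily episodes are excluded, and nothing supports 20% detection in those moved. It shows only that the sign is not guaranteed.
- **It may be a drafting slip.** As-treated efficacy with AE/SAEs excepted is the mirror image of common wording, and SAP 4.2.3 still contains template instructions. That is plausible, but the text still directs the wrong analysis and needs correcting.
- **Who is analysed is already fixed.** SAP 5.1.2 limits the primary analysis to those with 90-day follow-up. That is a separate matter; what is unsettled here is the arm in which each person is counted. Using 110 per arm changes the 19.0% above only to 17.9%.

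None of these points reconciles SAP 5.1 with protocol 8.2.

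**Conclusion.** The concern holds. As written, SAP 5.1 assigns participants in the primary and secondary comparisons by an undefined post-randomisation status, contrary to the protocol. This must be corrected before analysis because it leaves the arm assignment for the primary test open; the conclusion does not depend on the illustrated bias.

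The size of the effect cannot be determined from the documents. It is nil if receipt matches allocation, or if those moved have the same detection rate as everyone else under no true effect. In the illustrations, which assume one-way movement of 5–20% of the study arm, type I error ranges from 5% to 19%. With 10% moved, the planned 15-point difference becomes anything from 13.6 to 18.7 points.

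**What to change.** Replace the first sentence of SAP 5.1 with wording such as: *All primary, secondary, resource-use and serious-outcome analyses compare participants in the arm to which they were randomised, whether or not the device was received or used (intention to treat, protocol 8.2).*

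In SAP 6.4 items 4 and 7, describe the groups as those allocated to the recorder. Keep any as-treated analysis only as a labelled sensitivity analysis, with received defined by a fact recorded near randomisation (device issued and app set up), not by later use.

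Report device-related AEs under the arm allocated to the device. Delete the sentence that moves non-participants' AE/SAEs to control, or define taking part.

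The cost is SAP wording only. The main correction needs no new data and no protocol amendment. The optional sensitivity analysis needs device issue and set-up status. Neither document lists these among the data collected, so first confirm that site records hold them.
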